8.3.5 Potential for Infusion-Related Reaction

No infusion-related AEs with rovalpituzumab tesirine have been reported to date. However, as rovalpituzumab tesirine is administered via IV infusion, appropriate precautions should be taken during infusion of the drug with regular monitoring of vital signs per local institutional standards. In the event of a suspected infusion reaction, the infusion should be stopped at least temporarily and institutional standard supportive care administered.

Since nivolumab and ipilimumab contain only human immunoglobulin protein sequences, they are unlikely to be immunogenic and induce infusion or hypersensitivity reactions. However, if such a reaction were to occur, it might manifest with fever, chills, rigors, headache, rash, pruritis, arthralgias, hypo- or hypertension, bronchospasm, or other symptoms. All Grade 3 or 4 infusion reactions should be reported within 24 hours to the Medical Monitor and reported as an SAE if criteria are met. Infusion reactions should be graded according to NCI CTCAE version 4.03 guidelines.

Treatment recommendations are provided below and may be modified based on local treatment standards and guidelines as appropriate:

For Grade 1 symptoms: (Mild reaction; infusion interruption not indicated; intervention not indicated)

Remain at bedside and monitor subject until recovery from symptoms. The following prophylactic premedications are recommended for future infusions: diphenhydramine 50 mg (or equivalent) and/or paracetamol 325 to 1000 mg (acetaminophen) at least 30 minutes before additional nivolumab administrations.

For Grade 2 symptoms: (Moderate reaction requires therapy or infusion interruption but responds promptly to symptomatic treatment [e.g., antihistamines, non-steroidal anti-inflammatory drugs, narcotics, corticosteroids, bronchodilators, IV fluids]; prophylactic medications indicated for ≤ 24 hours).

Stop the nivolumab or ipilimumab infusion, begin an IV infusion of normal saline, and treat the subject with diphenhydramine 50 mg IV (or equivalent) and/or paracetamol 325 to 1000 mg (acetaminophen); remain at bedside and monitor subject until resolution of symptoms.

Corticosteroid or bronchodilator therapy may also be administered as appropriate. If the infusion is interrupted, then restart the infusion at 50% of the original infusion rate when symptoms resolve; if no further complications ensue after 30 minutes, the rate may be increased to 100% of the original infusion rate. Monitor subject closely. If symptoms recur then no further nivolumab or ipilimumab will be administered at that visit. Administer diphenhydramine 50 mg IV, and remain at bedside and monitor the subject until resolution of symptoms. The amount of study drug infused must be recorded on the electronic case report form (eCRF). The following prophylactic premedications are recommended for future infusions: diphenhydramine 50 mg (or equivalent) and/or paracetamol 325 to 1000 mg (acetaminophen) should be administered at least 30 minutes before additional nivolumab or ipilimumab administrations. If necessary, corticosteroids (recommended dose: up to 25 mg of IV hydrocortisone or equivalent) may be used.

For Grade 3 or Grade 4 symptoms: (Severe reaction, Grade 3: prolonged [i.e., not rapidly responsive to symptomatic medication and/or brief interruption of infusion]; recurrence of symptoms following initial improvement; hospitalization indicated for other clinical sequelae [e.g., renal impairment, pulmonary infiltrates]). Grade 4: (life-threatening; pressor or ventilator support indicated).

Immediately discontinue infusion of nivolumab or ipilimumab. Begin an IV infusion of normal saline, and treat the subject as follows. Recommend bronchodilators, epinephrine 0.2 to 1 mg of a 1:1,000 solution for subcutaneous administration or 0.1 to 0.25 mg of a 1:10,000 solution injected slowly for IV administration, and/or diphenhydramine 50 mg IV with methylprednisolone 100 mg IV (or equivalent), as needed. Subject should be monitored until the investigator is comfortable that the symptoms will not recur. Nivolumab or ipilimumab will be permanently discontinued. Investigators should follow their institutional guidelines for the treatment of anaphylaxis. Remain at bedside and monitor subject until recovery from symptoms. In the case of late-occurring hypersensitivity symptoms (e.g., appearance of a localized or generalized pruritis within 1 week after treatment), symptomatic treatment may be given (e.g., oral antihistamine, or corticosteroids).

8.3.6 Sponsor Safety Reporting to Regulatory Authorities

Investigators are required to report all SAEs, including anticipated SAEs, to the sponsor or designee (Section 8.2.2.7).

The sponsor or designee will report all SAEs to the appropriate regulatory authorities as required per local regulatory reporting requirements. In the United States, endpoints that assess disease-related mortality or major morbidity as well as other SAEs that are not study endpoints (but are known consequences of the underlying disease or condition that are anticipated to occur in the study population), should not be reported to Food and Drug Administration (FDA) as individual IND safety reports (per the final rule amending the IND safety reporting requirements under the Code of Federal Regulations 21 CFR 312.32 and FDA guidance, Safety Reporting Requirements for INDs and bioequivalence/ bioavailability (BE/BA) Studies, (FDA, 2012).

8.3.7 Laboratory Test Result Abnormalities

Any laboratory test result abnormality should be reported as an AE or SAE, as appropriate, if it:

- is clinically significant or meets the definition of an SAE
- required the subject to have study drugs discontinued or interrupted
- required the subject to receive specific corrective therapy

Wherever possible, the clinical rather than laboratory term should be used by the reporting investigator (e.g. "anemia" rather than "low hemoglobin").

8.3.8 Pregnancy

Pregnancy in a study subject must be reported to the sponsor within 1 working day of the site becoming aware of the pregnancy. Subjects who become pregnant during the study must be discontinued.

All subjects should be informed that contraceptive measures (refer to Section 5.10) should be taken throughout the study and for at least 31 weeks following the last dose of study drug. Male subjects should be informed that contraceptive measures should be taken by their female partner.

Information regarding a pregnancy occurrence in a study subject and the outcome of the pregnancy will be collected. In the event of a pregnancy occurring in the partner of an enrolled subject, written informed consent for release of medical information from the partner must be obtained prior to the collection of any pregnancy-specific information, and the pregnancy will be followed to outcome.

Pregnancy in a study subject is not considered an AE. However, the medical outcome of an elective or spontaneous abortion, stillbirth or congenital anomaly is considered a SAE and must be reported to AbbVie within 24 hours of the site becoming aware of the event.

8.4 Product Complaint

8.4.1 Definition

A Product Complaint is any Complaint related to the biologic or drug component of the products.

For a product this may include, but is not limited to, damaged/broken product or packaging, product appearance whose color/markings do not match the labeling, labeling discrepancies/inadequacies in the labeling/instructions (example: printing illegible), missing components/product, or packaging issues.

Any information available to help in the determination of causality to the events outlined directly above should be captured.

8.4.2 Reporting

Product Complaints concerning the investigational product must be reported to the sponsor within 24 hours of the study site's knowledge of the event via the Product Complaint form. Product Complaints occurring during the study will be followed-up to a satisfactory conclusion. All follow-up information is to be reported to the sponsor (or an authorized representative) and documented in source as required by the sponsor. Product Complaints associated with AEs will be reported in the study summary. All other complaints will be monitored on an ongoing basis.

Product Complaints may require return of the product with the alleged complaint condition. In instances where a return is requested, every effort should be made by the investigator to return the product within 30 days. If returns cannot be accommodated within 30 days, the site will need to provide justification and an estimated date of return.

The description of the complaint is important for AbbVie in order to enable AbbVie to investigate and determine if any corrective actions are required.

9. Data Quality Control and Quality Assurance

9.1 Site Training and Monitoring Procedures

A Study Binder with instructions for study compliance and eCRF completion will be provided. Prior to the enrollment of subjects at the site, the sponsor or its designated clinical and medical personnel will review the following items with the investigator and clinic staff:

- The protocol, study objectives, eligibility requirements, study procedures, registration and withdrawal processes
- Current IB
- Recording and reporting AEs and SAEs
- Enrollment goals and study timelines
- The eCRF completion process and source documentation requirements
- Monitoring requirements
- Institutional Review Board/Independent Ethics Committee (IRB/IEC) review and approval process
- Informed consent process
- GCP guidelines and related regulatory documentation requirements
- Key study team roles and responsibilities
- Investigational product storage, accountability, labeling, dispensing, and recordkeeping
- Subject coding
- Study samples/specimen collection, handling, and shipping
- Protocol compliance
- Clinical study record keeping, document retention, and administrative requirements

Monitoring visits will occur periodically, with frequency dependent on the rate of enrollment and workload at each site. During monitoring visits, the sponsor representative will review regulatory documentation, eCRFs, source documentation, investigational product storage, preparation, and accountability. The CRFs will be reviewed for completeness, adherence to the provided guidelines, and accuracy compared to the source documents. The investigators must ensure that the monitor is allowed to inspect all source documents pertinent to study subjects, and must cooperate with the monitor to ensure that any problems noted in the course of the trial are resolved. The investigator must maintain a comprehensive and centralized filing system of all study-related documentation that is suitable for inspection by the sponsor or its designated monitors and by quality assurance (QA) auditors, or representatives of regulatory authorities.

9.2 Data Management Procedures

The sponsor or its designee will provide eCRF Completion Guidelines for data entry. Study-specific data management procedures will be maintained in the Data Management Plan. Queries resulting from edit checks and/or data verification procedures will be posted in the eCRF.

9.3 Access to Source Data

The investigator will permit the sponsor's representatives to monitor the study as frequently as the sponsor deems necessary during or after the completion of the study to determine that protocol adherence and data recording are satisfactory. Appropriate measures to protect subject confidentiality are to be employed during monitoring. The eCRFs and related source documents will be reviewed in detail by the sponsor's representative(s) at each site visit. Original source documents or certified copies must be provided to the sponsor's representative for review. This review includes inspection of data acquired as a requirement for participation in this study and other medical records as required to confirm that the information contained in the CRFs, such as disease assessments, AEs, and concomitant therapies, is complete and correct. Other study records, such as correspondence with the sponsor and the IRB/IEC and screening and drug accountability logs will also be inspected. All source data and study records must also be made available during or after completion of the study for inspection by representatives of regulatory authorities. In the event of an inspection by regulatory authorities, the sponsor may be available to assist in any preparations. All pertinent study data must be made available as requested to the regulatory authority for verification, audit, or inspection purposes.

9.4 Accuracy and Reliability of Data

The sponsor or its designee shall take steps to assure the accuracy and reliability of data including:

- The selection of qualified investigators and appropriate study centers.
- Review of protocol procedures with the investigators and associated personnel prior to the study.
- Periodic monitoring visits by the designated monitor(s).
- Review of eCRFs for accuracy and completeness by the designated monitor(s) during monitoring visits to the study centers. Any discrepancies will be resolved with the investigator or designees as appropriate.

9.5 Quality Assurance Procedures

The sponsor's QA group or its designee may conduct audits at the clinical site or other study-related facilities and organizations during or at any time after the study. Audit reports will be retained by the sponsor's QA group or its designee as part of the written record.

9.6 Data Handling and Recordkeeping

9.6.1 Data Handling

It is the investigator's responsibility to ensure the accuracy, completeness, legibility, and timeliness of the data reported to the sponsor in the eCRFs and in all required reports. The eCRFs should be captured in the sponsor Electronic Data Capture (EDC) system within five (5) business days of the subject's visit to the site. Data reported on the eCRF that is derived from source documents should be consistent with the source documents or the discrepancies must be explained.

Any change or correction to an eCRF must be maintained in an audit trail within EDC system. Data changes may only be made by those individuals so authorized. Prior to database lock the investigator must review and approve the completed eCRFs to verify their accuracy.

9.6.2 Investigator Record Retention

The investigator shall retain study drug disposition records and all source documentation (such as original ECG tracings, laboratory reports, and in-patient or office subject records) for the maximum period required by the country and institution in which the study will be conducted, or for the following periods, whichever is longer: for at least two (2) years after the last approval of a marketing application in an ICH region and until there are no pending or contemplated marketing applications in an ICH region or for at least two (2) years after the relevant authority has been informed of the discontinuation of clinical development of the study drugs. The investigator may not destroy any records associated with the study without obtaining the prior, written consent of the sponsor. If the investigator withdraws from the study (due to relocation, retirement, etc.), the records shall be transferred to a mutually agreed upon designee, such as another investigator or IRB/IEC. No records shall be transferred without prior, written authorization from the sponsor or its designee.

10. Data Analysis and Statistical Methods

This section provides the key details of the statistical analyses to be performed using data captured according to this protocol. Further details on planned analyses for the data captured in this protocol will be provided in the Statistical Analysis Plan.

10.1 Determination of Sample Size

Up to approximately 90 subjects are expected to participate in this three-cohort trial (up to approximately 30 per cohort).

The primary objective of this study is to determine the tolerability, adverse event profile, and any DLTs for rovalpituzumab tesirine when given in combination with nivolumab or nivolumab and ipilimumab intravenously in adult subjects with extensive-stage small cell lung cancer. Safety will be monitored throughout the trial by the safety monitoring committee (SMC). The sample size for this study is based on the need to establish safety of the regimens being evaluated and 6 subjects is the minimum number required for the clinical safety evaluation of each cohort and 12 subjects may need to be enrolled in order to evaluate safety after 12 weeks in at least 6 subjects. Enrollment of a minimum of 6 subjects and a maximum of 30 subjects per cohort will allow for a preliminary evaluation of efficacy.

10.2 Analysis Populations

The following populations will be considered:

- Full Analysis Set: all enrolled subjects who receive any amount of study drugs.
- Safety Set: all subjects who receive any amount of study drugs.
- PK-Evaluable Set: all subjects who receive at least one dose of study drugs and for whom a baseline measurement and at least one blood sample following a dose of study treatment are available.

10.3 Planned Analyses

As a general strategy, continuous efficacy and safety endpoints will be summarized using the five-number summary (mean, standard deviation, median, minimum, and maximum). Frequency distributions (counts and percentages) will be used to summarize categorical endpoints.

10.3.1 Disposition of the Study Subjects

The disposition of subjects will be described with summaries by cohort of the number of subjects enrolled, the number of subjects treated, the number of subjects for whom study drugs were permanently discontinued (including the reasons for discontinuation), and the number of subjects who discontinued early from the study.

10.3.2 Demographic and Baseline Characteristics

Demographic and baseline characteristics will be summarized by cohort. Results will be reported using subjects in the full analysis set.

10.3.3 Exposure to Study Treatment

Frequency distributions of the number of received doses will be presented by cohort. Treatment duration for all enrolled subjects will be described by cohort.

10.3.4 Analysis of Efficacy Endpoints

ORR is defined as the proportion of subjects whose best overall response is either CR or PR according to RECIST v1.1. The number and percentage of responders along with the corresponding 95% confidence interval (CI) will be provided for each cohort.

CBR will be analyzed in a way similar to the analysis of the ORR (described above).

DOR will be summarized for responders (i.e., subjects with CR or PR only) by cohort. PFS and OS will be summarized by cohort. Median DOR, PFS, and OS will be obtained by using the Kaplan-Meier approach. The PFS rate at additional time points may also be evaluated (e.g., 26, 39, and 52 weeks). Details of the analysis of efficacy endpoints will be described in the Statistical Analysis Plan.

10.3.5 Safety Analyses

Safety endpoints will be summarized using data from the Safety Set. Safety analyses will involve examination of the incidence, severity, and type of TEAEs reported, changes in vital signs and laboratory test results from baseline (the assessment prior to first dose) to specified time points throughout the study, and concomitant medications use.

At least 1 laboratory or other safety-related assessment subsequent to at least 1 dose of study drug is required for inclusion in the analysis of a specific safety parameter. To assess change from baseline, a baseline measurement is also required.

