For each cohort and dose regimen, up to 30 total subjects may be enrolled as part of an expansion phase after evaluation of the tolerability of the first 6 evaluable subjects. Details regarding enrollment priorities are discussed in Section 3.1.

MAJOR ELIGIBILITY CRITERIA:

Subjects with histologically or cytologically confirmed, 2nd line or later extensive-stage SCLC with evaluable or measurable disease; Eastern Cooperative Oncology Group (ECOG) 0-1; adequate hematologic, hepatic, and renal function; no active, known, or suspected autoimmune disease; and no prior exposure to an immuno-oncology or pyrrolbenzodiazepine (PBD)-based drug.

PLANNED SAMPLE SIZE:

Up to approximately 90 subjects (up to approximately 30 subjects per cohort)

STUDY TESTS AND OBSERVATIONS:

Safety assessments (Section 2.4.1) include physical exam, vital signs, body weight, ECOG performance status, clinical adverse events (AEs), laboratory tests, electrocardiograms (ECGs), echocardiogram, Fluid Retention Questionnaire, and monitoring of concomitant medications.

Efficacy assessments will consist of radiographic imaging. Responses will be categorized by Response Evaluation Criteria in Solid Tumors (RECIST) v1.1 (Eisenhauer, 2009). See Section 6.4.6 for imaging schedule per cohort.

Blood samples for PK, immunogenicity, biomarker, and pharmacodynamics (PD) assessments will be collected at protocol-defined time points to support the study endpoints. Sensitive, validated assays will be used to measure blood concentrations of rovalpituzumab tesirine antibody-drug conjugate (ADC) and related analytes of rovalpituzumab tesirine, such as total antibody and SC-DR002, as applicable. A validated immunoassay will be used to assess ATA against rovalpituzumab tesirine. Analogous assays may be performed for nivolumab and/or ipilimumab.

Pharmacodynamic and biomarker assessments will include analyses of tumor tissue for DLL3 and PD-L1 expression, and of blood samples for tumor markers, circulating tumor cells (CTC), immune, and soluble biomarkers such as soluble DLL3.

STATISTICAL METHODS:

As a general strategy, data will be analyzed by cohort and dose regimen.

Safety analysis will include summaries by cohort and dose regimen of: AEs, laboratory measures, physical examinations, ECG, and vital signs using data from subjects in the Safety Analysis set. The incidence of DLTs will be summarized.

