2.4 Endpoints

2.4.1 Safety Endpoints

Analyses of the safety endpoints will include the following measurements or assessments:

- Adverse Events (AEs) and Dose-Limiting Toxicities (DLTs)
- Vital signs (Section 7.7.2)
- Body weight (Section 7.7.2)
- Laboratory abnormalities (Sections 7.7.3 and 8.3.7)
- Electrocardiographic parameters (e.g. QT interval corrected for heart rate [QTc], QT interval corrected for heart rate by Fridericia's formula [QTcF]) (Section 7.7.4)
- Echocardiography (Section 7.7.5)
- Eastern Cooperative Oncology Group (ECOG) performance status (Section 7.7.6)
- Monitoring of concomitant medications

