3.1 Summary of Study Design

This is a multicenter study involving rovalpituzumab tesirine administered in combination with nivolumab or nivolumab and ipilimumab in subjects with SCLC. The study plans to include 3 cohorts of up to approximately 30 subjects each (Table 1). DLTs will be assessed during the DLT Evaluation Period (Section 3.1.1).

Figure 1. Study Schema

- * Up to 12 DLL3+ subjects will be enrolled into each cohort in order to obtain 6 evaluable subjects at the end of the 12 week DLT period.
- a. Based on the tolerability of the initial 6 DLL3+ subjects in cohort 1, enrollment may begin of up to 12 DLL3+ subjects into cohort 2. The same strategy will be used for cohort 3 enrollment. If a regimen appears intolerable, the dose of rovalpituzumab tesirine may be reduced to 0.2 mg/kg, or 0.1 mg/kg. Such changes will constitute a new cohort, and subsequent cohorts may then carry forward the tolerated dose.
- b. For each cohort, up to 30 total subjects may be enrolled as part of an expansion phase after evaluation of the tolerability of the first 6 evaluable subjects.

Table 1. Planned Cohorts in the Study

Cohort	Population	Rovalpituzumab tesirine	Nivolumab	Ipilimumab
1	2 nd line or later SCLC (Platinum-failure) (Section 4.1)	0.3 mg/kg q6wk x 2	360 mg q3wk beginning on Week 4 (Cycle 2) x 2 cycles, then 480 mg q4wk	–
2	2 nd line or later SCLC (Platinum-failure) (Section 4.1)	0.3 mg/kg q6wk x 2	1 mg/kg q3wk x 4 cycles beginning on Week 4 (Cycle 2), then 480 mg q4wk (monotherapy) after 6 week washout	1 mg/kg q3wk x 4 beginning on Week 4 (Cycle 2)
3	2 nd line or later SCLC (Platinum-failure) (Section 4.1)	0.3 mg/kg q6wk x 2	1 mg/kg q3wk x 4 cycles beginning on Week 4 (Cycle 2), then 480 mg q4wk (monotherapy) after 8 week washout	3 mg/kg q3wk x 4 beginning on Week 4 (Cycle 2)

Initially, up to 12 subjects will be enrolled into Cohort 1 in order to obtain 6 evaluable subjects through the DLT evaluation period of 12 weeks. If $\leq 1/6$ subjects being evaluated has a DLT, enrollment beyond 12 subjects may proceed (i.e., enrollment into Cohort 1 expansion may begin). Subjects who are considered DLT-inevaluable (e.g., due to withdrawal from study before completing the DLT evaluation period; see Section 3.1.1) will be replaced if required.

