3.1.1 Definition of Dose-Limiting Toxicities

The DLT evaluation period is the first 12 weeks of treatment for all subjects. DLTs are defined as any of the following in the DLT-evaluation period, graded according to the National Cancer Institute's Common Terminology Criteria for Adverse Events (NCI CTCAE), version 4.03 (see Appendix 13.6)

- Grade 4 thrombocytopenia (or Grade 3 thrombocytopenia with bleeding) lasting more than 7 days and/or requiring platelet transfusion
- Grade 4 neutropenia lasting more than 7 days, and/or requiring hematopoietic growth factor rescue, or any febrile neutropenia (Grade 3 or 4 neutropenia with concurrent fever $\geq 38.3^{\circ}\text{C}$)
- Grade 4 anemia unrelated to underlying disease

- Clinically-significant Grade 3 or 4 non-hematologic laboratory abnormality that does not resolve to Grade 0/1 or baseline within 7 days
- Grade 3 or 4 non-laboratory AE with the exception of fatigue, asthenia, nausea, or other manageable constitutional symptom

The following events will not be considered DLTs:

- Any AE \geq Grade 3 clearly determined to be unrelated to study drug(s) (e.g., disease progression)
- \geq Grade 3 isolated alkaline phosphatase, amylase, or lipase laboratory abnormality of any duration
- \geq Grade 3 endocrinopathies controlled by hormone replacement
- Grade 3-4 electrolyte abnormalities

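### DLT incidence falls on the Safety Set, which keeps replaced DLT-inevaluable subjects, so the reported rate reads low and can disagree with the figure used at the ≤1/6 gate

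*Combined protocol and SAP*

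**What the plan says.** Section 2.4.1 puts DLTs, together with AEs, first in its list of safety endpoints. Section 10.3.5 gives one population for all such endpoints: "Safety endpoints will be summarized using data from the Safety Set". Section 10.2 defines it: "Safety Set: all subjects who receive any amount of study drugs". The only other sets in Section 10.2 are the Full Analysis Set and the PK-Evaluable Set. The Synopsis (Statistical Methods) refers to the Safety Analysis set and then adds "The incidence of DLTs will be summarized", without naming a different denominator.

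The design sections work on another basis. Section 3.1.1 says "The DLT evaluation period is the first 12 weeks of treatment for all subjects". Section 3.1 recognises DLT-inevaluable subjects; its example is "withdrawal from study before completing the DLT evaluation period; see Section 3.1.1) will be replaced if required". Section 10.1 allows for the loss: "12 subjects may need to be enrolled in order to evaluate safety after 12 weeks in at least 6 subjects". The rule for enrolling beyond 12 subjects (Synopsis and Section 3.1) is at most 1 DLT among 6 subjects being evaluated.

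**The concern.** The plan uses two denominators for one quantity. At the gate, a subject who leaves before week 12 is set aside and replaced. In the final table the same subject, if dosed, returns to the denominator. The Section 10.3.5 condition of at least one post-dose assessment would not remove someone who left in, say, week 3.

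Section 10.1 makes tolerability and DLTs part of the primary objective. A rate divided by partly observed subjects reads low. It may also differ, without explanation, from the figure the safety monitoring committee saw. Because results are presented by cohort, a regimen with more early loss would look better tolerated for that reason alone. Early loss is foreseeable, since the window is 12 weeks and the minimum life expectancy for entry (Section 4.1) is also 12 weeks.

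**Working it through.** **Inputs from the protocol.** 12-week window (3.1.1). Up to 12 enrolled for at least 6 evaluable (Synopsis, 3.1, 10.1). Gate of ≤1/6 (Synopsis, 3.1). Maximum of 30 per cohort (10.1). No attrition rate is stated, so the figure of 12 cannot be derived independently. It equals 6/(1 − 0.5), so it allows for an inevaluable share of up to 50%.

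**Step 1: worst case.** Suppose inevaluable subjects are all dosed and none has a DLT. Then Safety Set rate ÷ evaluable rate = evaluable ÷ treated, and the relative understatement is 1 − evaluable/treated.

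| Evaluable / treated | Understatement |
|---|---|
| 6/7 | 14% |
| 6/8 | 25% |
| 6/10 | 40% |
| 6/12 | 50% |
| 24/30 | 20% |
| 15/30 | 50% |

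At 6 of 12, with Clopper-Pearson 95% intervals:
- 1 DLT: 1/6 = 16.7% (0.4 to 64.1%) against 1/12 = 8.3% (0.2 to 38.5%).
- 2 DLTs: 2/6 = 33.3% (4.3 to 77.7%) against 2/12 = 16.7% (2.1 to 48.4%). A cohort that failed the gate would be tabulated at the passing percentage, 1/6.

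**Step 2: partial observation.** Assume a true 12-week risk of 25%, early leavers observed for half the window with half the risk (12.5%), and leaving unrelated to DLT risk. Take 12 treated subjects. The last column counts completers plus leavers with a DLT.

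| Leave early | Expected DLTs | Safety Set | Evaluable set |
|---|---|---|---|
| 3 (25%) | 9 × 0.25 + 3 × 0.125 = 2.625 | 2.625/12 = 21.9% | 2.625/(9 + 0.375) = 28.0% |
| 6 (50%) | 6 × 0.25 + 6 × 0.125 = 2.25 | 2.25/12 = 18.8% | 2.25/(6 + 0.75) = 33.3% |

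Against 25%, the Safety Set is 3.1 and 6.2 points low. The evaluable set is 3.0 and 8.3 points high.

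**Step 3: sensitivity.** Assume instead constant DLT and drop-out hazards λ and μ over the window, with time measured in windows. Then λ = −ln(1 − p), where p is the true risk. The expected Safety Set rate is d = λ/(λ+μ) × (1 − e^−(λ+μ)). The hazard μ is set so that completers plus subjects with a DLT, e^−(λ+μ) + d, make up 75% or 50% of those treated. For true risks of 10 to 40%, the Safety Set rate is about 85 to 86% of the truth at 25% inevaluable and 67 to 71% at 50%. At a true 25%, the evaluable-set rate is about 29% and 35% respectively.

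Both models give the same directions: Safety Set low, evaluable set high.

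**The case against.** The strongest reply is that no sentence explicitly divides DLTs by the Safety Set. The Synopsis line on DLT incidence names no denominator, Sections 10.3.5.1 to 10.3.5.7 contain no DLT analysis, and Section 10 leaves further detail to a Statistical Analysis Plan whose text is not in the document reviewed. An evaluable set could be defined there. This limits certainty but does not remove the point. Sections 2.4.1, 10.2 and 10.3.5 read together give one rule for all safety endpoints, and an evaluable denominator added later would depart from it.

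Second, an all-treated rate is a legitimate description if its numerator and denominator are shown, and the evaluable-set rate is not unbiased either. It keeps early leavers who had a DLT and drops those who did not. This stands. A reader might infer that changing the denominator recovers the true rate; Steps 2 and 3 show that it does not.

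Third, evaluability is never defined. Section 3.1 refers to Section 3.1.1, which gives the window and the events but no definition. If a subject who had a DLT and then withdrew were classed as inevaluable, the gap between the two rates would shrink or reverse. This also stands, and it is a reason to write the definition down.

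Fourth, Section 7.6 collects AEs for 100 days after study drug stops, longer than the 84-day window. A subject who stops treatment but stays in the study can therefore still be observed. The dilution comes mainly from withdrawal and death.

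**Conclusion.** The point holds for the reported DLT incidence. Under the half-window assumption, a true 25% rate reads about 22% with 25% early loss and 19% with 50%. Under constant hazards, the rate is about 14 to 15% low and 29 to 33% low in relative terms. These attrition levels are assumptions, because the protocol states only a maximum of 12 enrolled for 6 evaluable.

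Three stronger readings are not supported:
- **That the rate will be halved.** Half is a ceiling. It needs 6 of 12 subjects inevaluable, all dosed and none with a DLT.
- **That escalation or expansion decisions are distorted.** The ≤1/6 gate counts evaluated subjects, and the safety monitoring committee also reviews cumulative safety data (Section 3.1). No decision rule uses the final table.
- **That selection from passing the gate is part of this problem.** Pooling gate and later subjects in a cohort that passed has its own effect, but it would arise even if every subject were evaluable. The choice of analysis set does not cause it.

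The consequence is for interpreting a primary-objective result and comparing cohorts. It should be corrected before reporting.

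**What to change.** - **Section 10.2:** add a DLT-Evaluable Set, made up of subjects who complete the 12-week window or have a DLT within it. Use the same definition for the gate in Section 3.1.
- **Section 10.3.5 and Synopsis:** state that DLT incidence is reported by cohort on this set with an exact 95% CI, next to the Safety Set rate. Show numerators, denominators and the number of inevaluable subjects with reasons.
- **Interpretation:** state that the evaluable-set rate tends to read high and the Safety Set rate low, so the two are read together.
- **Statistical Analysis Plan:** carry the same definitions.

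The cost is one extra population and one extra table, with no added subjects or visits. The headline DLT rate will be less favourable and its interval wider: in the worst-case example, 4.3 to 77.7% instead of 2.1 to 48.4%.
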